GCP	Good Clinical Practice
GI	gastrointestinal
HR	hazard ratio
IC ₅₀	50% inhibitory concentration
ICF	informed consent form

Abbreviation	Full Term
ICH	International Conference on Harmonisation of Technical Requirements for Registration of Pharmaceuticals for Human Us
IDMC	Independent Data Monitoring Committee
IEC	Independent Ethics Committee
IND	investigational new drug
IRB	Institutional Review Board
ITT	intent-to-treat
i.v.	intravenous
IWG	International Working Group
JAK	Janus kinase
LCM	lower costal margin
LDH	lactate dehydrogenase
LVEF	left ventricular ejection fraction
MDS	myelodysplastic syndrome
MedDRA	Medical Dictionary for Regulatory Activities
MF	myelofibrosis
MPD	myeloproliferative disease
MPN-SAF TSS 2.0	Myeloproliferative Neoplasm-Symptom Assessment Form Total Symptom Score version 2.0
MRI	magnetic resonance imaging
MUGA	multigated acquisition scan
NCI	National Cancer Institute
PD	pharmacodynamic(s)
PET-MF	post-essential thrombocythemia myelofibrosis
РК	pharmacokinetic(s)
PMF	primary myelofibrosis
PPV-MF	post-polycythemia vera myelofibrosis
PRO	patient-reported outcome
PT	prothrombin time
PTT	partial thromboplastin time
PV	polycythemia vera
QD	once daily
QTc	corrected QT interval
RBC	red blood cell

Abbreviations

Abbreviation	Full Term
REB	Research Ethics Board
SAE	serious adverse event
SAP	statistical analysis plan
SGOT	serum glutamic-oxaloacetic transaminase (syn: see AST)
SGPT	serum glutamic pyruvic transaminase (syn: see ALT)
SMQ	Standardized MedDRA Query
STAT	signal transducers and activators of transcription
SVR	spleen volume reduction
TEAE	treatment-emergent adverse event
T _{max}	time of maximum concentration
TSS	total symptom score
TT	thrombin time
ULN	upper limit of normal
uMPD	unclassifiable myeloproliferative disease
US	United States
WOCBP	Woman of child-bearing potential
WBC	white blood cell

Abbreviations

1 Background Information

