There is no formal hypothesis to be tested in this study. Efficacy, safety, and PK/PD data will be summarized by dosage group using descriptive statistics. The dose–response and dose-exposure-response relationship will be explored using a modeling approach.

References

Harrison C, Kiladjian J-J, Kathrin H, et al. JAK inhibition with ruxolitinib versus best available therapy for myelofibrosis. N Engl J Med 2012;366:787-98.

 Table 1. PAC203 Study Assessments Calendar²⁰

Week	Consent and Screen ¹	Randomization and Start of Week 1 (Baseline) ²	End of Week 4 ³	End of Week 12 ⁴	End of Week 24 ⁴	Post -24 Week Follow Up Assessments	End of Treatment ⁵	30 Day Post End of Treatment ²¹
Day	-35 to -7	1	28	84	168	At 3-month intervals following Week 24 visit (ejection fraction assessment will be done at 6-month intervals)		+30 days from End of Treatment
Window (d)		-1	+/-3	+/-7	+/-7	+/-7	+/-7	+/-3
Informed consent ⁶	х							
Medical history	х							
Vital signs ⁷	х	х	Х	х	х	х	х	
Physical exam, including spleen measurement ⁸	х	х	х	х	х	x	х	
12-lead ECG ⁹	х	х	Х	х	х	x	х	х
Ejection fraction assessment (Echo or MUGA)	x		х	x	х	x	x	x
ECOG performance status	х		Х	х	х	х	х	
Hematology ¹⁰	х	х	Х	x	х	х	х	Х
Coagulation testing	х	х	Х	х	х	x	х	Х
Serum chemistry ¹¹	х	х	As clinically indicated					
Serum pregnancy test ¹²	X		Х	X	X		х	
Spleen volume by MRI (preferred modality) or CT ^{1, 13}	x			x	X	x	X	

 Table 1. PAC203 Study Assessments Calendar²⁰

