¹ Screening procedures must be completed between Days -35 and -7, before treatment initiation, with the exception of the screening (baseline) MRI or CT scan, which must be parformed between Days -10 and -4								
² Day 1 assessments are required to be performed prior to initiation of study treatment and can be performed up to 24 hours prior to initiation of study treatment. At the baseline visit, all patients will be provided with a prescription (and instructions to fill that prescription) for loperamide (Imodium) or a similarly effective antidiarrheal drug. Patients will be instructed to start taking the prescribed loperamide or other antidiarrheal drug per package and physician instructions as soon as they notice any change in frequency or consistency of bowel movements after starting study treatment.								
³ The study visit at week 4 has a scheduling window of ±3 days; however, all procedures other than MRI or CT should be performed on the same day's visit within ±24 hours. ⁴ The study visits at weeks 12 and 24 have a scheduling window of ±7 days; however, all procedures other than MRI or CT should be performed on the same day's visit within ±24 hours.								

Table 1. PAC203 Study Assessments Calendar²⁰

- ⁵ The End of Treatment visit is scheduled within 7 days after terminating study treatment. A final visit to assess events is scheduled 30 ±3 days after the last dose of study treatment. If treatment ends at a regularly scheduled visit, these procedures may be performed at that time.
- ⁶ Informed consent must be obtained before any study-specific washout. This may require 2 weeks (A 2-week washout will be required for anticoagulation agents, antiplatelet agents (except aspirin doses of ≤ 100 mg/day), strong CYP3A4 inhibitors, strong CYP450 inducers, and QTc prolonging agents) or 28 days if patient was taking any experimental therapies. Patients not requiring washout may sign the Informed Consent Form at any time prior to screening procedures.
- ⁷ Vital signs include blood pressure, pulse, respiratory rate, temperature, and body weight.
- ⁸ Height should be measured only at baseline. Spleen size assessed by physical examination as the distance below the LCM at the midclavicular line.

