- ⁹ A single 12-lead ECG (collected in triplicate) will be performed at screening and *within* 1 hour prior to dosing and *at* 4 hours (± 10 minutes) post dosing on Day 1 of week 1 and at the end of weeks 4, 12, and 24, 30 days postterm, and as clinically indicated. ECGs will also be collected pre-dose during the post 24-week follow-up visits within 1 hour prior to dosing. The ECGs will be read centrally by blinded independent cardiologist.
- ¹⁰ Hematology includes CBC, differential, platelet count and hemoglobin A1C. For patients with baseline platelet count of \leq 50,000/µL, platelet count will be monitored weekly for the first 8 weeks, then monthly if counts remain \leq 50,000/µL. These platelet counts must be analyzed by the central laboratory, but local laboratory test results may be used for assessment and management of patients in real time. Samples collected for local testing must also be submitted to the central laboratory and the results captured in the clinical database. Additional hematology testing should be done as clinically indicated.
- Eligibility may be based on local or central laboratory values. Central serum chemistry values will include: ALT/SGPT, AST/SGOT, alkaline phosphatase, bilirubin (total, direct, and indirect) creatinine, LDH, sodium, potassium, chloride, bicarbonate, calcium, phosphate, magnesium, BUN/urea, albumin, amylase, lipase, glucose, cholesterol, uric acid, and high sensitivity CRP. Any samples collected at any visits must be analyzed by the central laboratory, although local laboratories may additionally be used for patient assessment and management in real time.
- ¹² All women of child-bearing potential (WOCBP) must have a pregnancy test at screening. For WOCBP in the UK, the screening pregnancy test must occur no longer than 7 days before the first study drug administration and again at the End of Week 4 visit. Additional pregnancy tests every 12 weeks while on study treatment may be mandated as a country-specific requirement.

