The screening evaluations listed below are to be carried out **between 35 and 7 days prior to the start of treatment**, with the exception of MRI or CT scan, which must be performed between 10 and 4 days prior to the start of the study.

- Medical history
- Vital signs, including pulse, systolic and diastolic blood pressure, respiratory rate, temperature, and body weight
- Physical examination, including spleen measurement
- 12-lead ECG (collected in triplicate)
- Ejection fraction assessment (Echocardiogram or MUGA)
- ECOG performance status
- Hematology: CBC with differential, platelet count and hemoglobin A1C

- Coagulation testing including PT, INR, PTT, and TT
- Serum chemistry, including ALT/SGPT and AST/SGOT, alkaline phosphatase, bilirubin (total, direct, and indirect), creatinine, LDH, sodium, potassium, chloride, bicarbonate, calcium, phosphate, magnesium, BUN/urea, albumin, amylase, lipase, glucose, cholesterol, uric acid, and high specificity CRP
- Serum pregnancy test for women of childbearing potential (WOCBP). For WOCBP in the UK, the screening pregnancy test must occur no longer than 7 days before the first study drug administration. If fertile, males and females must agree to use effective birth control methods during the study. Women of childbearing potential must use highly effective methods (defined as those resulting in a failure rate of <1% per year when used consistently and correctly) for the duration of study treatment and for 12 months after last dose of study drug. The contraceptive methods considered highly effective are intrauterine devices and hormonal contraceptives (contraceptive pills, implants, transdermal patches, hormonal vaginal devices, or injections with prolonged release). Males must use a condom for the duration of the study and for 90 days after the last dose of study treatment. When abstinence is used as a method of birth control, only true abstinence is acceptable, when this is in line with the preferred and usual lifestyle of the patient. Periodic abstinence (calendar, ovulation, symptothermal, and post-ovulation methods) and withdrawal are not acceptable methods of contraception.

- MRI (preferred) or CT scan (without contrast) for measurement of spleen volume (to be performed between Days -10 and -4 prior to the start of treatment).

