- Begin collecting patient-reported disease-related symptoms on MPN-SAF TSS 2.0 via electronic diary. Patient must complete daily for 7 consecutive days prior to starting treatment.
- Baseline symptoms and AEs
- Concomitant medications
- Transfusion history (RBC and platelets)

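### Outside the UK, the only pregnancy test required before first dose may be up to 35 days old, and none is scheduled at baseline

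*Protocol*

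**What the plan says.** Four parts of the protocol decide when the pre-dose pregnancy test is done.

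- **Who is tested.** Footnote 12 to Table 1: "All women of child-bearing potential (WOCBP) must have a pregnancy test at screening".
- **When screening happens.** Footnote 1: "Screening procedures must be completed between Days -35 and -7, before treatment initiation". Section 7.1.4, whose list includes the pregnancy test, gives the same window: "between 35 and 7 days prior to the start of treatment". Both name one exception, the MRI or CT scan.
- **The UK rule.** Footnote 12, repeated in Section 7.1.4: "For WOCBP in the UK, the screening pregnancy test must occur no longer than 7 days before the first study drug administration".
- **Baseline.** The Table 1 row "Serum pregnancy test" is empty in the baseline column, and the Section 7.1.5 list for that visit contains no pregnancy test.

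The protocol also has safeguards. Inclusion criterion 13 and Section 7.1.4 ask fertile patients to use effective birth control during the study. Section 7.1.4 adds: "Women of childbearing potential must use highly effective methods", meaning a failure rate under 1% per year, and sets the period as "for the duration of study treatment and for 12 months after last dose of study drug". Exclusion criterion 22 bars pregnant women.

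**The concern.** Pregnancy is an absolute exclusion, and Section 4.2.1 lists it as a reason to stop treatment. The test that enforces the exclusion can nevertheless be five weeks old when dosing starts. ECG, hematology, coagulation and chemistry are all repeated at the baseline visit; pregnancy is not. The protocol already contains a tighter standard but applies it in one country. Drug, doses and exclusion criterion are the same everywhere, and the documents give no scientific reason for the difference.

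At stake is first exposure of an unrecognized pregnancy to an investigational kinase inhibitor. It could arise because the pregnancy was too early to show at screening, or because conception followed through contraceptive failure or non-use. This is a participant-safety matter and does not touch the analysis.

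**Working it through.** The plan states no figure for this, so the check sets the rules side by side and counts days.

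**1. Age of the test at first dose**

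| Setting | Governing text | Days before first dose |
|---|---|---|
| Outside the UK, as written | Footnote 1, Section 7.1.4 | 7 to 35 |
| UK rule | Footnote 12, Section 7.1.4 | 0 to 7 |
| All countries, with the fix | UK rule extended | 0 to 7 |
| Repeat on the baseline draw | Footnote 2 (up to 24 hours before dosing) | at most 1 |

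If a Day 0 were counted between Day -1 and Day 1, the Table 1 window alone would read 8 to 36 days. Section 7.1.4 counts back from the start of treatment and settles it at 7 to 35.

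**2. Other required tests before dosing.** There are none. The extra tests that footnote 12 allows some countries to mandate take place during study treatment, after the first dose.

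**3. Contraceptive failure between test and first dose.** Take the upper limit of 1% per year from Section 7.1.4, applied as a constant rate under correct use:

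- 7 days: 0.01 × 7/365 = 0.019% per woman
- 35 days: 0.01 × 35/365 = 0.096% per woman

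**4. Number of women.** The documents give no number of women of childbearing potential and no country split. Assume they are 1% to 5% of about 150 patients, with 50% to 100% of them outside the UK:

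- low: 0.01 × 150 × 0.5 = 0.75
- high: 0.05 × 150 × 1.0 = 7.5

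That is about 1 to 8 women.

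**5. Expected pregnancies from method failure alone**

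- low: 0.75 × 0.00019 = about 0.0001
- high: 7.5 × 0.00096 = about 0.007

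Failure of a correctly used method is therefore a negligible part of the risk. What remains is a pregnancy too early to show at screening, or non-use of contraception. The documents offer no basis for estimating either.

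**The case against.** The strongest reply is that the risk is tiny and already managed. The birth-control agreement sits within the Section 7.1.4 screening list. A highly effective method has to be in place by the time treatment starts. Randomization requires every eligibility criterion to be met, including exclusion 22, and a site may retest if the baseline examination raises suspicion. The countable part of the risk comes to at most about 0.007 pregnancies across the trial. Amendment 6 is also late: it ends study treatment at and beyond Week 24, and the documents do not say whether anyone remains to be screened.

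Much of this stands, and it limits the weight of the point. But contraception prevents pregnancy and does not detect it. Read literally, the highly effective rule is dated from study treatment, so the days before first dose rest on the general birth-control rule. Exclusion 22 has no timely test behind it, and a voluntary retest is not a requirement. On timing, the current text still plans about 150 patients. If screening has closed, the change belongs in the next pacritinib protocol.

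Two stronger readings are tempting, and the documents support neither:

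- **That the protocol contradicts itself on later tests.** Table 1 marks Weeks 4, 12, 24 and End of Treatment, while Section 7.1.6 limits Week 4 to the UK and Sections 7.1.7 and 7.1.8 test only where a country mandates it. But the Table 1 row carries footnote 12, which says who is tested and broadly matches those sections. The Table 1 note that patients complete all visits through Week 24 is about following those who stop treatment or progress. These tests also come after dosing.
- **That UK sites face an unworkable rule.** Read literally, the general window and the UK limit share only Day -7. A site can simply follow the specific rule. The symptom diary in the same list also runs past Day -7 without a named exception: "Patient must complete daily for 7 consecutive days prior to starting treatment". This is untidy wording and poses no safety risk.

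**Conclusion.** The point holds as a modest safety improvement. A site outside the UK that follows the plan exactly may give the first dose on a pregnancy test 7 to 35 days old, with no recheck. That follows directly from the text and needs no assumption. The estimate of about 1 to 8 women does rest on assumed shares, and no figure can be given for how many might be pregnant at first dose. A reader should not infer any effect on dose selection, endpoints or analyses; there is none. The case for change is that the possible harm is serious, the stricter rule already exists in the protocol, and extending it costs very little.

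**What to change.** - In footnote 12 and Section 7.1.4, extend the UK rule to all women of childbearing potential: a negative pregnancy test within 7 days before first dose, with the result known before dosing.
- In footnote 1 and Section 7.1.4, name the pregnancy test beside MRI/CT as an exception to the Day -7 cut-off. This also tidies the UK wording.
- Let sites comply in either of two ways. They can time the screening test within 7 days of first dose, which needs no extra assay. If the screening test is older than that, they can repeat it on the baseline draw with a local result, which Section 9.2 allows for eligibility and treatment decisions.
- In the baseline column of Table 1 and in Section 7.1.5, add the test as conditional: only if the screening test is more than 7 days before first dose. An unconditional baseline entry would remove the option that needs no extra assay.

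The cost is protocol wording, at most one extra assay per woman, and a possible short wait for the result. A test within 7 days reduces the chance of missing a very early pregnancy but does not eliminate it.

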1.1 JAK2 in Hematologic Malignancies

The Janus kinases (JAK) are a family of cytoplasmic tyrosine kinases consisting of JAK1, JAK2, JAK3, and TYK2. They play a pivotal role in the signaling pathways of numerous cytokines, hormones, and growth factors. Their intracellular substrates include the signal transducer and activator of transcription (STAT) family of proteins. The JAK/STAT pathways, through the proper actions of the ligands, regulate important physiological processes, such as the immune response to viruses, hematopoiesis, lactation, and lipid homeostasis. However, dysfunctional signaling caused by a myriad of factors results in pathological conditions, such as allergies, asthma, rheumatoid arthritis, severe combined immune deficiency, and hematological malignancies. In particular, mutations in the JAK2 gene have been associated with myeloproliferative disorders (MPDs), including polycythemia vera (PV), essential thrombocythemia (ET), and idiopathic myelofibrosis (MF).

The incidence of the JAK2V617F mutation, as determined by allele-specific polymerase chain reaction in granulocytes from patients with MPDs, occurs in 35% to 50% of patients with primary MF (PMF), 32% to 57% of patients with ET, and 74% to 97% of patients with PV. This mutation, however, can also be found on rare occasions in patients with other chronic myeloid diseases, including myelodysplastic syndromes (MDS), MDS/MPDs, and unclassifiable MPD (uMPD). There is strong evidence that the JAK2 mutation (and corresponding continuously active JAK2 tyrosine kinases) significantly contributes to the existence and progression of the disease. Its inhibition thus presents a suitable target for drug development. Even in patients without JAK2 mutation, the JAK/STAT pathway may be deregulated, and these patients may also benefit from JAK2 inhibitor therapy.

1.2 Myelofibrosis

1.2.1 Clinical Presentation and Disease-Related Symptoms

MF may present as either a primary myeloproliferative disorder or follow a diagnosis of PV or ET. Regardless of the original diagnosis, PMF, post-polycythemia vera MF (PPV-MF), and post-essential thrombocythemia MF (PET-MF) have a common pathophysiological profile, characterized by elevated numbers of CD34-positive cells in the marrow in the early phase of the disease, followed in the later phases by marrow fibrosis, with decreasing numbers of CD34 cells in the marrow and a corresponding increase in splenic and liver engorgement by CD34 cells.

PMF, PPV-MF and PET-MF usually present with a white blood cell (WBC) count <30,000/mm³, prominent teardrops on peripheral smear, normocellular or hypocellular marrow with moderate to marked fibrosis, an absence of the Philadelphia chromosome or the BCR-ABL translocation, and frequent positivity for the *JAK2* mutation (Campbell and Green 2006). In addition to the clonal proliferation of a multipotent hematopoietic progenitor cell, an event common to all chronic MPDs, these disorders are characterized by colonization of extramedullary sites, such as the spleen or liver (Barosi 1999, Tefferi 2000).

About 70% of patients with MF are symptomatic at presentation. The main physical findings are splenomegaly and hepatomegaly. Other symptoms include those secondary to a hypercatabolic state (fever, weight loss, and night sweats) and peripheral blood abnormalities (fatigue and dyspnea resulting from anemia and bleeding; petechiae resulting from thrombocytopenia and/or abnormal platelet function). Gout and renal stones secondary to hyperuricemia are also common (Ahmed and Chang 2006). Other clinical manifestations of the disease include thromboembolic episodes, hemorrhage, splenic pain, early satiety, anemia, and bone pain.

PMF, PPV-MF, and PET-MF have similar types and distributions of bone marrow cytogenetic abnormalities (Tefferi et al 2001), and they are known to harbor a common mutant allele, *JAK2V617F* (James et al 2005).

Transformation from PV to PPV-MF significantly worsens survival. *JAK2* mutations are almost always present in patients with PV and PPV-MF. Common clinical and laboratory findings in PPV-MF include a hyperproliferative bone marrow, National Cancer Institute (NCI) Common Terminology Criteria for Adverse Events (CTCAE, version 4.0) grade 2 to 3 marrow fibrosis, anemia, splenomegaly, and constitutional symptoms (Passamonti et al 2008).

Diagnostic tools for PMF, PPV-MF, and PET-MF include complete blood count (CBC), bone marrow aspiration and biopsy, cytogenetic analysis, peripheral blood smear analysis for teardrop-shaped red blood cells (RBCs), the number and kinds of WBCs, platelet count, and the presence of blast cells.

1.2.2 Current Strategies for Treating PMF, PPV-MF, and PET-MF

Currently, as no therapeutic strategy has been efficacious at reducing overall mortality, medical therapy for PMF, PPV-MF, and PET-MF is administered with supportive intent. Treatment is aimed at improving quality of life through palliation of symptoms and control of peripheral blood counts (Arana-Yi et al 2006). Therapeutic interventions usually are used only in symptomatic patients with MF, since asymptomatic patients demonstrate prolonged survival (Barosi 1999, Dupriez et al 1996).

At present, allogeneic stem cell transplantation (ASCT) is the only available method for altering the natural history of PMF, PPV-MF, or PET-MF (Passamonti et al 2008, Rondelli et al 2005). ASCT can completely reverse the fibrosis in bone marrow (Ni et al 2005) and restore normal hematopoiesis. However, while ASCT is potentially curative for patients with PMF, PPV-MF, and PET-MF, this form of treatment is largely limited to young patients with negligible comorbidities (Arana-Yi et al 2006). The International Working Group (IWG) – Myelofibrosis Research and Treatment considers it "…reasonable to recommend ASCT for high- or intermediate-risk 2 patients" (Cervantes et al 2009). Thus far, no therapy has proven effective in prolonging overall survival (OS) in PMF, PPV-MF, or PET-MF (Arana-Yi et al 2006).

Current treatment approaches are aimed at mitigating specific disease symptoms, such as anemia. Transfusion therapy is the core strategy for treatment of disease-related anemia, and it is also used to manage thrombocytopenia. Long-term RBC transfusion therapy should be accompanied by oral iron chelation therapy to avoid long-term consequences of iron overload. Disease-associated anemia occasionally responds to erythropoietin, hydroxyurea, cladribine, thalidomide, lenalidomide, or interferon treatment (Ahmed and Chang 2006). These and other agents have been used to correct cytopenias, halt the progression of splenomegaly, or reduce the size of a site of extramedullary hematopoiesis in patients with PMF, PPV-MF, and PET-MF.

Danazol, a synthetic attenuated anabolic steroid with androgenic activity, has been used to treat anemia in PMF, PPV-MF, and PET-MF. Erythropoietin has been administered to patients with these diseases for palliation of constitutional symptoms and anemia (Arana-Yi et al 2006). The use of interferon- α can result in hematologic responses, including reduction in spleen size, but many patients do not tolerate this medication (Sacchi 1995, Gilbert 1998). Antiangiogenic and immunomodulatory drugs, such as thalidomide and lenalidomide, have shown activity in patients with MF (Gilbert 1998, Barosi et al 2002, Marchetti et al 2004, Tefferi et al 2006, Mesa et al 2004, Strupp et al 2004), but they are not routinely used for the indications proposed in this study of pacritinib.

Other antiangiogenic agents, such as vatalanib and sorafenib, have been studied in PMF, PPV-MF, and PET-MF, but the data are not promising. Etanercept has been evaluated, but it was not superior to the combination of thalidomide and prednisone (Arana-Yi et al 2006).

The use of signal transduction inhibitors, such as imatinib, have resulted in an increase in the number of clonogenic megakaryocytic progenitors in bone marrow, suggesting they may be an effective treatment for thrombocytopenia in patients with MF (le Bousse-Kerdiles et al 2005).

For patients with PMF, PPV-MF, or PET-MF who have painful splenomegaly and no other treatment options, splenectomy may be performed. The decision to perform splenectomy involves weighing the benefits (long-term improvement in symptomatic splenomegaly, anemia, portal hypertension, and severe thrombocytopenia in 30% to 70% of patients) versus the risks (10% postoperative mortality, and 30% postoperative morbidity caused by infection, bleeding, or thrombosis; additionally, some investigators have reported accelerated progression to blast crisis).

